TITLE	Multicentric clinical investigation on the use of single-dose ophthalmic solution based on sodium hyaluronate in the treatment of eye discomfort in particular in case of ocular dryness
CLINICAL INVESTIGATION CODES	052/SI Hyalistil Bio PF Mono
AMENDMENT	052/SI Hyalistil Bio PF Mono/EM version 1 of March 14th, 2023
AIM OF THE CLINICAL INVESTIGATION	To assess the performance and safety resulting from the treatment of an ophthalmic solution for the ocular discomfort and in particular in presence of ocular dryness.
CLINICAL INVESTIGATION SITES	
1) P.O. San Marco, Azienda Ospedaliero Universitaria Policlinico "G. Rodolico - San Marco" Oculistica, [name], [name] (Italy)
 
[name] [contact] Email: [contact]
 
2) U.O. di Oculistica, Presidio Belmonte, Azienda Ospedaliero Universitaria Policlinico "Paolo Giaccone" [name], [name] (Italy)
 
[name] [contact] Email: [contact]

CLINICAL INVESTIGATION PHASE	Post Market Clinical Follow up (PMCF) (Investigator sponsored per profit, prospective, observational, non-interventional clinical investigation)
CLINICAL INVESTIGATION PERIOD	Approximately 4 months from first patient first visit (FPFV) to last patient last visit (LPLV) Each patient enrolled will be treated for 35 ± 4 days. Enrollment period: 3 months.
CLINICAL INVESTIGATION DESIGN	Multicenter, prospective, observational, open-label, non- interventional clinical investigation evaluating the performance and safety of 4 daily instillations of the ophthalmic solution in the treatment of mild irritation of the ocular surface.
CLINICAL	28 male and female subjects with signs and symptoms of ocular

INVESTIGATION POPULATION	discomfort and ocular irritation resulting from ocular dryness who qualifies for Hyalistil Bio PF treatment.
NUMBER OF SUBJECTS	28 subjects recruited with competitive enrolment at the involved study sites.
SUBJECT SELECTION CRITERIA	
Inclusion criteria
 
1. Subjects (male or female) must be ≥ 18 years of age;2. Subject able to provide Informed Consent, in compliance with the good clinical practice and local laws (thus, subject able to comprehend the full nature and purpose of the study, including possible risks and side events);3. Subjects with ocular discomfort resulting from mild to moderate dry eye in one or both eyes determined by:
- Scoring of ocular surface staining with fluorescein using the National Eye Institute (NEI) scale. Total score per single eye range 6-33 summing the score of cornea and conjunctiva. (Considering a normal score of 0-33);- Tear film break-up time with fluorescein (TFBUT) ≤ 10 seconds; The TFBUT value will be recorded as the average of 3 measurements;- Symptom Assessment in Dry Eye (SANDE) questionnaire ≥ 35.4. Subject able to be compliant with the requirements of the clinical investigation plan, according to the Investigator;5. Subject who qualifies for Hyalistil Bio PF treatment according to the approved indication;6. Subject who in physician's opinion will benefit from this treatment. 
Exclusion criteria
 
1. Corneal injuries or abrasions of traumatic origin in the eye of study;2. Ocular infection or clinically significant inflammation (such as Herpes Simplex infection, corneal virus infection, bacterial, viral or fungal conjunctivitis, tuberculosis and mycosis of the eye, purulent and herpetic blepharitis, stye);3. Sjögren's syndrome;4. Stevens-Johnson syndrome;5. Systemic lupus erythematosus;6. Pathologies associated with corneal thinning;7. Taking drugs that may interfere with tear gland secretion (beta - blockers);8. Patients using any topical therapies such as non-steroidal anti-inflammatory drugs, cortisone, cyclosporine, vasoconstrictor, artificial tears (different than the investigated product) the eye of study;

Hyalistil Bio PF Mono
Medical device

Study code: 052/SI Hyalistil Bio PF Mono

	
9. Treatment with topical or systemic corticosteroids in the 4 weeks preceding the study;
 
10. Known or potential hypersensitivity and/or history of allergic reactions to one of the components of the topical medical device.
 
11. Participation in another clinical trial within the previous 30 days;
 
12. Evidence of severe or uncontrolled systemic disease or any other significant disorders, which in the opinion of the Investigator does not allow the participation in the study or could compromise the results.

CLINICAL INVESTIGATION OBJECTIVES	
PRIMARY OBJECTIVE
 
• Evaluation of Tear film break-up time with fluorescein (TFBUT) at Study Termination Visit (Day 35 ± 4 of treatment) compared to Visit 1 (Day 0 of treatment - baseline). 
SECONDARY OBJECTIVE
 
• Evaluation of the change in total score (score from 6 to 33, considering a normal score 0-33) resulting from the sum of the corneal staining score (score from 0 to 15) and conjunctival staining score (score from 0 to 18) with fluorescein using the National Eye Institute Scale (NEI) at Visit 2 (Day 14 ± 2 of treatment) and at the Study Termination Visit (Day 35 ± 4 of treatment) compared to Visit 1 (Day 0 of treatment - baseline);• To evaluate the tear film stability per group as objectified by the tear break up time with fluorescein (TFBUT) at Study Termination Visit (Day 35 ± 4 of treatment) compared to Visit 2 (Day 14 ± 2 of treatment).• Changes about Best Corrected Visual Acuity (BCVA) measured by the “Early Treatment Diabetic Retinopathy Study” (ETDRS) at Visit 2 (Day 14 ± 2 of treatment) and Study Termination Visit (Day 35 ± 4 of treatment) compared to Visit 1 (Day 0 of treatment - baseline).• Patient reported outcomes: To compare patients reported outcomes (PRO) measures per group, including:
- Patient's reported symptoms (SANDE) at Visit 2 (Day 14 ± 2 of treatment) and Study Termination Visit (Day 35 ± 4 of treatment) compared to Visit 1 (Day 0 of treatment - baseline).- Assessment of the quality of life (QOL)### by “Questionnaire about Eye Symptoms and Daily Life” (DEQS) at Study

	
Termination Visit (Day 35 ± 4 of treatment) compared to Visit 1 (Day 0 of treatment - baseline). - Evaluation of the degree of satisfaction to the treatment reported by patients through the use of the visual analogue scale (VAS)^{##}, at the Study Termination Visit (Day 35 ± 4 of treatment). ###In the event that, for both trial centers, the DEQS questionnaire is not available, the assessment of the quality of the life will be performed by the DEQ-5 questionnaire.
 
SAFETY EVALUATIONS
 
 • Evaluation of the safety and the compliance of medical device.
ENDPOINTS[^]	
PRIMARY ENDPOINTS[#]
 
 • Clinical performance: 
 - 25 30% increase from Visit 1 (Day 0 of treatment - baseline) to Study Termination Visit (Day 35 ± 4 of treatment) of tear film break-up time with fluorescein (TFBUT)[◊]. [Time frame: Visit 1 and Study Termination Visit]. 
SECONDARY ENDPOINTS
 
 • Reduction from baseline (Visit 1- Day 0 of treatment) in the corneal and conjunctival fluorescein staining score using the NEI scale. Fluorescein staining of the ocular surface is assessed as the total sum of the corneal and conjunctival subregions. 
 - Corneal Fluorescein Staining (NEI score, sum of 5 subregions, maximum score 15. Each subregion will have a maximum score of 3. (0=no staining, 3 = maximum staining). - Conjunctival Fluorescein Staining (NEI score, sum of 6 subregions, maximum score 18. Each subregion will have a maximum score of 3. (0=no staining, 3 = maximum staining). [Time frame: Visit 1, Visit 2 and Study Termination Visit]. • Tear film break-up time with fluorescein (TFBUT)[◊]. [Time frame: Visit 2 and Study Termination Visit]. • BCVA is measured using the standard Early Treatment Diabetic Retinopathy Study (ETDRS) acuity chart and reported in ETDRS letters. [Time frame: Visit 1, Visit 2 and Study Termination Visit]; • Patient reported outcomes: 
 - Change in intensity and frequency of dry eye symptoms assessed by completing the questionnaire SANDE. [Time frame: Visit 1, Visit 2 and Study Termination Visit]. - ##Evaluation of the degree of satisfaction to the treatment reported by patients through the use of the visual analogue scale (VAS) ^{##}, ranging from 0 to 100 mm, at Study Termination Visit (Day 35 ± 4 of treatment).

	
treatment). [Time frame: Study Termination Visit]. Patients will be asked to rate their degree of satisfaction to the treatment and answer the following questions:
 
• “I feel satisfied using this treatment? ”,• “With this treatment, I have a feeling of freshness? ”,• “With this treatment, I have a feeling of relief? ”,• “This treatment contributed to reduce my pain due to eye dryness? ”,• “This treatment is comfortable? ”, 
Patients will be asked to place a vertical mark on a horizontal line, from 0 to 100 mm, to indicate the degree of satisfaction to the treatment, where:
 
✓ 0-10 mm=none ✓ 11-30 mm=very mild ✓ 31-50 mm=mild ✓ 51-70 mm=moderate ✓ 71-90 mm=strong ✓ 91-100 mm=very strong.
 
-Assessment of the quality of life (QOL) by “Questionnaire about Eye Symptoms and Daily Life” (DEQS)### at Study Termination Visit (Day 35 ± 4 of treatment) compared to Visit 1 (Day 0 of treatment - baseline). [Time frame: Visit 1 and Study Termination Visit].
 
###In the event that, for both trial centers, the DEQS questionnaire is not available, the assessment of the quality of the life will be performed by the DEQ-5 questionnaire
 
EVALUATION OF SAFETY PARAMETERS
 
✓ Evaluation of safety of daily instillation of ophthalmic solution during all the study period through:
 
• Investigator Global Assessment of Safety (IGAS): using the 4-point scale: 1 = very good safety, 2 = good safety, 3 = moderate safety and 4 = poor safety. IGAS will be evaluated at the Study Termination Visit. [Time Frame: Study Termination Visit];• Evaluation of reported adverse events/incidents. [Time Frame: During the treatment period].• Evaluation of intraocular pressure (IOP). [Time frame: Visit 1, Visit 2 and Study Termination Visit];• Evaluation of compliance through verification of correct instillation of the medical device, counting of single dose containers and boxes. [Time Frame: Visit 2 and Study Termination Visit]. 
^According to clinical practice, the Investigator will perform all clinical

--	---

	
evaluations on both eyes of the individual patient.
 
In the case that both eyes are affected by ocular dry eye, the statistical analysis will be performed considering the eye with the lowest level of TFBUT score “worse eye”. If the level of TFBUT score at baseline is the same in both eyes, then the eye with the highest level of NEI score will be designated as the “worse eye.”
 
If the level of NEI score at baseline is the same in both eyes, then the right eye will be designated as the “worse eye.”
 
#The primary end point will be evaluated on the PP population and also in ITT population.

STATISTICS	
Sample size estimate
 
A previous study report baseline level of tear film break-up time with fluorescein (TFBUT) of 6.23 ± 1.75 at baseline, to detect a 25% increase of TFBUT at the Study Termination Visit compared to baseline (Visit 1) (mean difference 1.56, sd 1.91), with an alpha=0.01(two-tailed) and a power $(1 - \beta)$ of 0.80, 23 subjects are required (Wilcoxon signed-rank test). Considering a dropout of 20%, it is expected to enroll a total of 28 subjects.
 
Statistical analysis
 
Descriptive analysis will be performed by using absolute rate, percentage and frequency tables for qualitative variables.
 
Normally distributed data will be reported as minimum, maximum, means and standard deviations, whereas non-normally distributed data as medians and interquartile range (IQR).
 
To compare qualitative variables for not-paired data will be used the Chi-square test with Yates corrections or Fisher's exact test when appropriate and the McNemar's test for paired data.
 
Differences in endpoints between baseline and different timepoints will be assessed using paired t-test for normally distributed data, whereas the Wilcoxon signed-rank test will be used for non-normally distributed data.
 
Data distribution will be tested by using the Kolmogorov-Smirnov test. A p-value <0.05 will be considered statistically significant.
 
All the Analysis will be performed using SAS version 9.4 for Windows (SAS Institute Inc., Cary, NC, USA).
 
Analysis set
 
All patients enrolled will be included in the safety population.
 
All patients enrolled having a primary post-baseline -performance assessment will be included in the ITT population.
 
If the primary performance measurement at Visit 2 is missing, it will be imputed with the score at baseline. If the primary performance

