The Informed Consent will be reviewed, discussed, dated and signed by both the subject and the Investigator before the beginning of screening procedures. Each subject will be interviewed by the Investigator who will record medical history, previous/concomitant pharmacological treatments, and will conduct a routine medical examination.

No laboratory tests are planned.

The data subject (including personal data and special categories of personal data) will be processed only by the authorised scientific staff, as reported in the staff signature and the delegation log.

The Investigator will assign two progressive numerical codes (screening number) to the screened patient and (subject clinical investigation number) to the enrolled patient.

The Investigator will not assign subjects into intervention groups and will not be made any attempts to collect data beyond those available throughout the course of normal clinical practice. Only the authorised scientific staff will know any additional information regarding the identifiability of the patient. The Sponsor and/or the delegated staff of CRO will receive and/or known anonymized patient data through the numerical code (unique subject identifiers code) assigned by the Investigator.

The unique subject identifiers code consists of the 5-digit screening number (e.g. S1001, S1002,...S1028 etc.), and, if applicable, the 4-digit subject clinical investigational number (e.g. 1001, 1002, 1028, etc.). Specifically, the first subject clinical investigational number was referred to the study site.

Allocation screening number and subject clinical investigational number are separated by slashes (e.g. “S1001/1001”). (e.g. “S1001/1001” for site number 1, “S2001/2001” for site number 2).

The Investigator will only report the information and data in coded form in the clinical study record, referring exclusively to the unique subject identifiers code assigned to the patient at the time of enrolment.

In the unlikely event that authorized staff of CRO becoming aware of the patient's identity or parts of their identity, the CRO can neither transcribe/ report/ copy nor save this information or even communicate or transmit to the Sponsor.

The Investigator and the Sponsor are autonomous data controllers.

4. Clinical Investigation Design

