- #Evaluation of the degree of satisfaction to the treatment reported by patients through the use of the visual analogue scale (VAS)^{##}, ranging from 0 to 100 mm, at Study Termination Visit (*Day 35 ± 4 of treatment*). [Time frame: Study Termination Visit].

Patients will be asked to rate their degree of satisfaction to the treatment and answer the following questions:

- “I feel satisfied using this treatment? ”,
- “With this treatment, I have a feeling of freshness? ”,
- “With this treatment, I have a feeling of relief? ”,
- “This treatment contributed to reduce my pain due to eye dryness? ”,
- “This treatment is comfortable? ”,

Patients will be asked to place a vertical mark on a horizontal line, from 0 to 100 mm, to indicate the degree of satisfaction to the treatment, where:

✓ 0-10 mm=none

Study code: 052/SI Hyalistil Bio PF Mono

- ✓ 11-30 mm=very mild
- ✓ 31-50 mm=mild
- ✓ 51-70 mm=moderate
- ✓ 71-90 mm=strong
- ✓ 91-100 mm=very strong.

- Assessment of the quality of life (QOL) by “Questionnaire about Eye Symptoms and Daily Life” (DEQS) at Study Termination Visit (Day 35 ± 4 of treatment) compared to Visit 1 (Day 0 of treatment - baseline). [Time frame: Visit 1 and Study Termination Visit].

###In the event that, for both trial centers, the DEQS questionnaire is not available, the assessment of the quality of the life will be performed by the DEQ-5 questionnaire.

Evaluation of safety parameters

Evaluation of safety of daily instillation of ophthalmic solution during all the study period through:

- Evaluation of safety of daily instillation of ophthalmic solution during all the study period through:
- Investigator Global Assessment of Safety (IGAS): using the 4-point scale:1= very good safety, 2 =good safety, 3 = moderate safety and 4 = poor safety. IGAS will be evaluated at the Study Termination Visit. [Time Frame: Study Termination Visit];
- Evaluation of reported adverse events/incidents. [Time Frame: During the treatment period].
- Evaluation of intraocular pressure (IOP) [Time frame: Visit 1, Visit 2 and Study Termination Visit];
- Evaluation of *compliance* through verification of correct instillation of the medical device, counting of single dose containers and boxes. [Time Frame: Visit 2 and Study Termination Visit].

[^]According to clinical practice, the Investigator will perform all clinical evaluations on both eyes of the individual patient.

The statistical analysis will be performed considering right eye as the “study eye.”

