3.3. Safety Evaluations

- Evaluation of safety of daily instillation of ophthalmic solution during all the study period through:
 - ✓ Investigator Global Assessment of Safety (IGAS): using the 4-point scale: 1 = very good safety, 2 = good safety, 3 = moderate safety and 4 = poor safety. IGAS was evaluated at the Study Termination Visit. [Time Frame: Study Termination Visit];
 - ✓ Evaluation of reported adverse events/incidents. [Time Frame: During the treatment period];
 - ✓ Evaluation of intraocular pressure (IOP) [Time frame: Visit 1, Visit 2 and Study

Termination Visit];

According to clinical practice, the Investigator will perform all clinical evaluations on both eyes of the individual patient.

In the case that both eyes are affected by ocular dry eye, the statistical analysis will be performed considering the eye with the lowest level of TFBUT score “worse eye”. If the level of TFBUT score at baseline is the same in both eyes, then the eye with the highest level of NEI score will be designated as the “worse eye”. If the level of NEI score at baseline is the same in both eyes, then the right eye will be designated as the “worse eye.”

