10.2 Definitions, Derived Variables and Datasets

10.2.1 Baseline Values

Study code: 052/SI Hyalistil Bio PF Mono

Data collected at the screening/baseline visit (Visit 1), before the beginning of the treatment, are considered as baseline values.

The last observation carried forward method (LOCF) was used to replace missing data in each performance endpoints.

Baseline and demographic characteristics of the patients will be summarized by using appropriate descriptive statistics.

For more details see paragraph 11.1.

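### Where the study eye is the one with the lower Visit 1 TFBUT, that reading is also the baseline, so the uncontrolled primary increase includes regression to the mean

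*Protocol*

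**What the plan says.** **Choice of eye.** In the Endpoints footnote of the protocol synopsis, when both eyes are affected, "the statistical analysis will be performed considering the eye with the lowest level of TFBUT score". Ties are settled on baseline values: "If the level of TFBUT score at baseline is the same in both eyes, then the eye with the highest level of NEI score" is taken, and then the right eye. SAP 3.3 and 5.2 carry the same rule ("In the case that both eyes are affected by ocular dry eye, the statistical analysis will be performed considering the eye with the lowest level").

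**A competing rule.** The footnote to protocol section 19 and SAP 5.3 both say: "The statistical analysis will be performed considering right eye as the" study eye. Neither document says which rule governs.

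**Baseline.** Visit 1 is screening, enrolment and baseline in one. SAP 10.2.1 says: "Data collected at the screening/baseline visit (Visit 1), before the beginning of the treatment, are considered as baseline values". No second pre-treatment reading is scheduled. Eligibility rests on the same visit: "Tear film break-up time with fluorescein (TFBUT) ≤ 10 seconds", in one or both eyes.

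**Comparison.** There is no control group. Protocol section 3 states: "The Investigator will not assign subjects into intervention groups". SAP 13.1 tests the change from Visit 1 to the Study Termination Visit with a paired t-test or Wilcoxon signed-rank test, and the shell for SAP Table 4.1.1 sets the null value at zero. The percentage change is tabulated descriptively in Table 4.1.2. The significance level is 0.05.

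**Data available.** Protocol section 19 says that "the Investigator will perform all clinical evaluations on both eyes of the individual patient". TFBUT is measured at all three visits. Neither document mentions regression to the mean, an analysis of both eyes, or any adjustment.

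**The concern.** One Visit 1 value does three jobs: it admits the patient, selects the eye and serves as the baseline. The lower of two noisy readings tends to be low partly because of that day's measurement error or fluctuation. That part does not persist, so the selected eye is expected to read higher at the next visit without any treatment effect. A concurrent control selected in the same way would show the same rise, and the comparison would cancel it. This study has no control, and the test asks only whether the change differs from zero.

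At stake is the primary result. The shift always favours the product, would be read as performance, and can by itself make p<0.05 much more likely than the nominal level suggests.

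**Working it through.** **1. The plan's own figure.** The target is 25% × 6.23 = 1.56 s, with SD of change 1.91, two-sided alpha 0.01 and power 0.80. The normal approximation gives ((2.576 + 0.842) × 1.91/1.56)² = 17.5, so 18. The noncentral t gives 21. Dividing by the Wilcoxon efficiency 3/π gives 21 × π/3 = 22.0. The stated 23 is consistent with this, and n = 23 is used below.

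**2. Inputs.**
- From the documents (protocol section 23, SAP 7): mean 6.23 s, SD 1.75 s, target 1.56 s. From protocol section 6: entry at 10 s or below.
- Assumed, because the documents give no values: the correlation r between visits for the same eye, 0.5–0.9; the correlation ρ between the two eyes at one visit, 0.5–0.7, with ρ no greater than r; all patients bilateral; visit noise independent between eyes.
- The SDs 1.75, 2.06 and 1.91 would imply r = (1.75² + 2.06² − 1.91²)/(2 × 1.75 × 2.06) = 0.51. But 1.91 is also the pooled value √((1.75² + 2.06²)/2), so it is not evidence about r.

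**3. Closed form, ignoring the entry cut-off.** The lower of two eyes lies on average SD × √((1−ρ)/π) below the mean. A fraction (1−r)/(1−ρ) of that gap is visit noise and does not persist. The expected rise with no treatment effect is therefore

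SD × (1−r) / √(π(1−ρ)).

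For r = 0.7, ρ = 0.5: 1.75 × 0.3/√(3.1416 × 0.5) = 0.525/1.253 = 0.42 s. For r = 0.9, ρ = 0.5: 0.175/1.253 = 0.14 s. For r = ρ = 0.5: 0.875/1.253 = 0.70 s.

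**4. Simulation with the 10 s cut-off.** There is no treatment effect; the last column is a paired t-test at n = 23, counting increases with p<0.05 (nominal 2.5%).

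| r | ρ | Rise (s) | % of worse-eye baseline | % of 1.56 s | Significant increases |
|---|---|---|---|---|---|
| 0.5 | 0.5 | 0.71 | 13 | 46 | 53–54% |
| 0.7 | 0.5 | 0.43 | 8 | 28 | 33–34% |
| 0.7 | 0.7 | 0.55 | 10 | 35 | 53% |
| 0.8 | 0.7 | 0.37 | 7 | 24 | 36–37% |
| 0.9 | 0.7 | 0.18 | 3 | 12 | 19–20% |
| 0.9 | 0.5 | 0.14 | 3 | 9 | 13–14% |

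The simulated worse-eye baseline is about 5.45 s at ρ = 0.5 and 5.60 s at ρ = 0.7. The two rows with r = ρ are boundary cases in which the eyes have no lasting difference.

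**5. Relaxing the two strong assumptions.** If only half the patients are bilateral, the mean shift roughly halves. If half the visit noise is common to both eyes (r and ρ unchanged), choosing the lower eye can pick out only the other half, and the shift again roughly halves. Over the same grid, either change gives about 0.08–0.39 s and 6.5–18% significant increases.

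**6. Alternatives.** Averaging both eyes leaves 0.01–0.03 s and about 3% significant increases. A pre-fixed right eye also leaves only the cut-off's contribution, at most 0.03 s. That contribution is small because 10 s lies (10 − 6.23)/1.75 = 2.2 SD above the planning mean.

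**The case against.** **The size is assumed, not known.** This stands. The correlations, the share of bilateral patients and the sharing of noise between eyes are all absent from the documents. The top of the range needs every patient bilateral, independent noise and no lasting difference between eyes. A reader might infer that about half of all trials of an inert product would succeed. The documents do not support that: one-eye entry is allowed, and plausible changes in two assumptions bring the rate to 6.5–18%.

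**The endpoint is a 25% increase.** This stands in part. A reader might infer that regression to the mean could deliver the stated target. The expected shift is at most about 13% of the worse-eye baseline. In simulation a 25% mean rise occurred in a few per cent of trials at the extreme pair (0.5, 0.5) and practically never elsewhere. The planned test, however, is against zero, so a small shift is enough for p<0.05. Applying the sample-size alpha of 0.01 does not cure this: with all patients bilateral, 4–28% of no-effect trials would still show a significant increase, against a nominal 0.5%.

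**The right eye may be the study eye.** This stands. If protocol section 19 and SAP 5.3 govern, the bias from eye selection is gone. It would be wrong to read the bias as unavoidable; it depends on which rule is applied.

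**Averaging three readings and the 10 s measurement limit protect the result.** These do not stand. Averaging within a visit reduces reading noise but not variation between days. Capping the termination reading at 10 s changes the bias by less than 0.01 s.

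**Conclusion.** The concern holds wherever the worse-eye rule is applied. The selecting reading is the baseline, there is no comparator, and the change is tested against zero, so the expected primary change is positive with no treatment effect. The direction follows from the documents; the size does not.

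Under the assumptions listed, the built-in rise is about 0.14–0.71 s, with 13–54% false significant increases. With half the patients bilateral, or half the visit noise shared, it is about 0.08–0.39 s and 6.5–18%. A reader might conclude that any observed increase is an artefact. That goes too far: the shift is below half of the planned 1.56 s throughout. What is compromised is the meaning of p<0.05 and the part of the increase that can be credited to the product.

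**What to change.** State one rule that does not select the eye on the baseline reading, and use it throughout both documents. For each patient, take the mean TFBUT over all eyes that met the entry criteria at Visit 1 (both if both qualify, otherwise the single eye), at Visit 1 and at the Study Termination Visit. Put this in the protocol synopsis and in SAP 5 and 13.1. Reconcile SAP 3.3, protocol section 19 and SAP 5.3 with it, so that the worse-eye and right-eye statements no longer compete.

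Keep the worse-eye analysis as a labelled sensitivity analysis, and state in the report that its change includes regression to the mean. The averaged analysis is still an uncontrolled before–after change and should be described as such.

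Timing needs care. The SAP is dated October 10th 2023, and SAP section 4 gives last patient last visit as August 3rd 2023, in an open-label study. The change should be made before database lock and recorded as an amendment (protocol section 22.4) or as a deviation in the final report (SAP 14), with the reason given.

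The cost is a documented change to the primary analysis, one further analysis run and probably a smaller observed increase. No new data are needed, because both eyes are measured at every visit.
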